A prospective, non-randomized, minimally invasive, cohort case-control study includes patients (men and women) aged ≥ 40 years. Participants will be recruited from 01.11.2023 to 10.06.2024 at the University Clinical Hospital No. 1 of Sechenov University, Moscow.

Once enrolled in the study, participants will be divided into two groups based on the results of a stress computed tomography myocardial perfusion (CTP) imaging with vasodilation test using the adenosine triphosphate:

- The first group is planned to include 31 people with myocardial perfusion defect on the stress computed tomography myocardial perfusion Imaging (by using contrast enhanced multi-slice spiral computed tomography (CE-MSCT) using adenosine triphosphate (ATP)).

- The second group is planned to include 49 people without myocardial perfusion defect on the stress computed tomography myocardial perfusion imaging (by using contrast enhanced multi-slice spiral computed tomography (CE-MSCT) using adenosine triphosphate (ATP)).

All patients are planned to undergo the following examinations:

1. Exhale into proton transfer reaction- time of flight-mass spectrometry-1000 for one minute using the PTR-TOF-MS-1000 device (Patients/control group come to the hospital (ate two hours before the test to avoid hypoglycemia during the stress test)/did not brush their teeth with toothpaste).

To prepare the participant for the time-of-flight mass spectrometry with proton transfer ionization method, the participant enters the office, sits on a chair in front of the device, the patient is informed that he/she needs to clasp the breathing tube with his/her lips, breathe through the nose and exhale through the mouth into the tube, which is connected to the PTR-TOF-MS-1000 device (IONICON PTR-TOF-MS - Trace VOC Analyzer, [name] (Europe)), for 1 minute.

2. After the procedure of exhaled air analysis in PTR TOF-1000, patients undergo a bicycle ergometry study, according to the Bruce protocol or the modified Bruce protocol). Then, immediately after stopping the load test, patients undergo a repeated study of exhaled air by the method of time-of-flight mass spectrometer with ionization by the proton transfer method for 1 minute, and after 3 minutes a repeated analysis of exhaled air is carried out, also for 1 minute. The obtained exhaled breath data will be analyzed using machine learning models.

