3. On the morning of study enrollment, a single 10 mL venous blood sample will be collected via peripheral venipuncture using vacuum biochemical tubes from all participants. The samples will undergo centrifugation at 2000 rpm for 20 minutes to separate plasma, after which the plasma fraction was aliquoted into seven sterile tubes using calibrated pipetting systems. Each tube will be labeled with the participant's unique registration number and sample collection date, then sealed within individual bags displaying duplicated identification data externally. Samples were cryopreserved at -82 to -84°C in ultra-low temperature freezers for long-term storage. Following complete blood collection across the cohort, frozen plasma specimens will be transferred to the laboratory for quantification of total cholesterol (TC), low-density lipoprotein (LDL), very low-density lipoprotein (VLDL), high-density lipoprotein (HDL), triglycerides (TG), lipoprotein(a), apolipoprotein B (ApoB), C-reactive protein (CRP), and interleukin-6 (IL-6).

4. Before and immediately after the exercise test, all patients are scheduled to have a single-channel ECG and pulse wave recorded using a portable single-channel recorder (Cardio-Qvark) (Russia, Moscow). Single lead ECG with pulse wave parameters will be analyzed using machine learning models.

5. All participants will undergo CTP with vasodilation test.

5. The object of the study and the planned number of observations, with justification for the selection of patients.

The object of the study is 80 human.

Inclusion Criteria:

1. Age \geq 40 years;
2. Absence of acute exacerbations of psychiatric disorders or cognitive impairments that would preclude study participation;
3. Provision of written informed consent for study participation, blood sample collection, and anonymous publication of research results;
4. Pre-test probability of ischemic heart disease between 1% and 33%.

Non-inclusion criteria:

1. Pregnancy and breastfeeding;
2. Diabetes mellitus;
3. Presence of acute myocardial ischemia (acute coronary syndrome or myocardial infarction within the preceding 48 hours) or a history of myocardial infarction;
4. Active infectious or non-infectious inflammatory diseases in the acute/exacerbation phase;

5. Connective tissue diseases (regardless of disease activity);
6. Respiratory disorders (e.g., bronchial asthma, chronic bronchitis, cystic fibrosis, or other conditions associated with significant respiratory dysfunction);

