7. Acute pulmonary thromboembolism involving the pulmonary artery or its branches;
8. Aortic dissection;
9. Hemodynamically significant decompensated cardiac valvular defects;
10. Active malignancy;
11. Decompensated chronic heart failure (NYHA class III-IV) or acute heart failure;
12. Neurological disorders (e.g., Parkinson's disease, multiple sclerosis, acute psychosis, Guillain-Barré syndrome);
13. Cardiac arrhythmias or conduction abnormalities contraindicating stress testing;
14. Musculoskeletal disorders precluding exercise testing (e.g., bicycle ergometry);
15. Allergy to radiocontrast agents and/or adenosine triphosphate (ATP);
16. Chronic kidney disease with an estimated glomerular filtration rate (eGFR) <30 mL/min/1.73 m² (CKD-EPI formula);
17. Severe hepatic insufficiency and/or Child-Pugh class B or C liver cirrhosis.

Exclusion Criteria:

1. Poor recording quality of single-channel electrocardiogram (ECG) and/or plethysmography data;
2. Failure to complete the stress test due to reasons unrelated to cardiac conditions;
3. Voluntary withdrawal of consent to continue participation in the study;
4. Post-enrollment development of conditions or identification of pathologies listed in the exclusion criteria.

6. Evaluated outcomes (primary endpoints).

The results in the primary are subjective and subject to the objectivity of the study.

1. Assessing the diagnostic accuracy of the stress electrocardiography in the diagnosis of ischemic heart disease (AUC, Sensitivity, Specificity, Sensitivity, NPV, and PPV)
2. Analyze the volatile organic compounds of the exhaled breath in individuals with stress-induced myocardial perfusion defect on stress computed tomography myocardial perfusion imaging (CTP) with vasodilation test (adenosine triphosphate) and compare them with individuals without stress-induced myocardial perfusion defect after a physical stress test, and compare them with rest results as independent variables. Machine learning model will be used to assess the diagnostic accuracy of the exhaled breath in the diagnosis of ischemic heart disease

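### Exclusion item 4 cites a list that names no pathology; read as the non-inclusion list, it lets conditions provoked or first revealed by the study tests remove participants from the accuracy analysis

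*Protocol*

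**What the plan says.** Protocol section 5 has two separate lists: 17 non-inclusion criteria, which name diseases, and four exclusion criteria for people already enrolled.

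- Exclusion item 4 removes a participant for "Post-enrollment development of conditions or identification of pathologies listed in the exclusion criteria".
- The other three exclusion items cover poor single-channel ECG or plethysmography recordings, withdrawal of consent, and (item 2) "Failure to complete the stress test due to reasons unrelated to cardiac conditions".
- The non-inclusion list contains, among others, item 3 ("Presence of acute myocardial ischemia (acute coronary syndrome or myocardial infarction within the preceding 48 hours) or a history of myocardial infarction"), item 11 ("Decompensated chronic heart failure (NYHA class III-IV) or acute heart failure") and item 13 ("Cardiac arrhythmias or conduction abnormalities contraindicating stress testing").

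Section 4 forms the comparison groups after enrolment: "Once enrolled in the study, participants will be divided into two groups based on the results of a stress computed tomography myocardial perfusion (CTP) imaging". The planned sizes are 31 with a perfusion defect and 49 without. Section 6 makes the diagnostic accuracy of stress ECG the first primary endpoint, followed by exhaled breath and single-lead ECG.

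**The concern.** In a diagnostic accuracy study, who stays in the analysis should not depend on what the tests under study, or the reference standard, did to the patient or showed. Item 4 has no such safeguard. A participant whose exercise test triggers an acute coronary event, or whose CTP shows an infarct nobody knew of, can be removed after those results are known. If the people removed differ in test positivity from those who stay, sensitivity, specificity and AUC are biased. This would affect both the stress-ECG benchmark and the new markers meant to improve on it. Two staff members could also decide the same case differently, because the list that item 4 points to is not the list it needs and its relation to item 2 is not stated.

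**Working it through.** **1. The cross-reference.** The four exclusion items are recording quality, incomplete test for a non-cardiac reason, withdrawal of consent, and item 4 itself. None is a pathology. Taken literally, item 4 removes nobody. It has content only if it means the 17 non-inclusion criteria.

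**2. Which listed conditions a study test can provoke or reveal.**

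| Non-inclusion item | Route |
|---|---|
| 3, acute coronary syndrome or infarction | provoked by exercise |
| 3, history of infarction | unrecognised infarct first seen on CTP |
| 11, acute heart failure | provoked by exercise |
| 13, arrhythmia or conduction abnormality | possibly, if a rhythm provoked by the test is held to contraindicate testing |

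Item 3 restricts acute ischaemia to acute coronary syndrome or infarction. An ordinary positive exercise ECG, or an inducible perfusion defect, does not trigger it.

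**3. Timing.** Exercise and CTP are study procedures for enrolled participants, and the CTP result defines the groups. Item 4 covers both development and identification of a condition, with no end date. An old infarct seen on CTP could therefore place a patient in the defect group and also remove that patient.

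**4. Items 2 and 4 side by side.** Item 2 excludes an incomplete test only when the reason is not cardiac. By implication, a cardiac stop is not a ground for exclusion. If that stop was an acute coronary syndrome, item 4 read with non-inclusion item 3 removes the patient. Neither item says which prevails.

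**5. Size.** The plan's own figures agree: 31 + 49 = 80. It gives no event rate, expected sensitivity or allowance for exclusions, so the effect can only be illustrated.

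Inputs: 31 CTP-positive patients (section 4); sensitivity 70% (assumed); k = 2 or 4 removed (assumed); 31 taken as the count before removal (assumed, because the plan does not say). Expected true positives: 0.70 × 31 = 21.7.

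- All k true positives: (21.7 − k)/(31 − k)
- All k false negatives: 21.7/(31 − k)

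| k | all true positives | all false negatives |
|---|---|---|
| 2 | 19.7/29 = 67.9% | 21.7/29 = 74.8% |
| 4 | 17.7/27 = 65.6% | 21.7/27 = 80.4% |

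With whole-number counts, k = 3 and other assumed sensitivities:

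- From 16/31 = 51.6%: 13/28 = 46.4% or 16/28 = 57.1%.
- From 25/31 = 80.6%: 22/28 = 78.6% or 25/28 = 89.3%.

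If the patients removed have the same positivity rate as those who stay, sensitivity does not shift. Without replacement, three CTP-positive removals lower the diseased share from 31/80 = 38.8% to 28/77 = 36.4%, which also moves PPV and NPV.

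For scale, the exact 95% interval for 22/31 (71.0%) is 52% to 86%.

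**The case against.** The strongest reply is that item 4 mostly enforces eligibility. History of infarction is a non-inclusion condition, and the endpoints concern stress-induced defects, so removing someone later found to have an old infarct preserves the intended population. This carries weight. Keeping such patients does alter the population slightly, and for that reason the fix includes a sensitivity analysis without them. It does not answer the case of a condition that the study test itself provokes.

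The other side is also right that four stronger readings, each of which a reader might infer, lack support:

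- *Items 2 and 4 contradict each other.* Item 2 does not say that patients stopped for cardiac reasons are kept; it only does not exclude them. Exclusion criteria add to one another, so this is an unresolved tension.
- *Patients with the clearest ischaemic response are removed, so sensitivity is understated.* The wording of non-inclusion item 3 leaves the ordinary test-positive patient untouched, and the table shows that the shift can go either way.
- *Item 13 plainly covers exercise-induced arrhythmia.* It more naturally means a rhythm that bars the test beforehand, so it is only a possible route.
- *A high CRP or IL-6 would remove a participant through non-inclusion item 4 and so inflate specificity.* That item concerns "Active infectious or non-infectious inflammatory diseases in the acute/exacerbation phase", a clinical state. The documents set no CRP or IL-6 threshold and do not link the batch assays back to eligibility.

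Finally, part of the SAP was not available for this assessment, so an analysis-set definition there cannot be ruled out. Protocol item 4 would need correcting even so.

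**Conclusion.** The point holds in limited form. The cross-reference is defective on any reading. On the only workable reading, item 4 permits exclusion that depends on index-test or reference-standard results, and nothing in the available text exempts such cases, defines the accuracy analysis set or ranks item 2 against item 4.

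The number affected is probably small and is not given. In the 70% illustration, two to four removals move sensitivity by between −4.4 points (70.0 to 65.6) and +10.4 points (70.0 to 80.4). Those extremes require every removed patient to be of one kind. Most of these shifts are small beside the sampling uncertainty with 31 diseased patients, but a larger sample would not correct them. The documents do not establish a direction of bias.

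**What to change.** For the analysis set only:

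1. Correct item 4 so that it refers to the non-inclusion criteria.
2. Limit removal under item 4 to conditions present before the first study test and established from information other than the study tests.
3. Keep in the accuracy analysis all available data from participants whose condition arose during or after the study tests or was first revealed by them. Add a sensitivity analysis that leaves out those found to have had a pre-existing non-inclusion condition, such as an old infarct.
4. Reconcile items 2 and 4 so that one stated rule governs the analysis of tests stopped for a cardiac reason.
5. Report every post-enrolment exclusion by reason, with its index-test and CTP results where available.

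The cost is a wording change, one extra analysis and a reporting table, all from data already collected. The small downside is that a few atypical patients stay in the primary analysis. This concerns retention in the analysis, not how such patients are handled clinically or whether they continue testing.

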The algorithms employ statistical methods including descriptive statistics, Student's t-test, chi-square test, ROC analysis, Shapiro-Wilk test, Mann-Whitney U test, Kruskal-Wallis test, Fisher's test, McNemar test and Lasso regression. Continuous variables express as mean \pm standard deviation for normal distribution or as medians for skewed distribution. Categorical variables are expressed as frequencies and percentages. The Kolmogorov-Smirnov test use to determine whether continuous variables were normally distributed. The relationships between quantitative variables test using Pearson or Spearman correlation, depending on the type of distribution. Analysis of differences in means between continuous variables of two categories perform using the Student's (Welch) t-test or the Mann-Whitney U-test, as appropriate; categorical variables were analyzed using the χ^2 test (or Fisher's exact test if this was not applicable). To assess the relationship between continuous variables of more than two categories, analysis of variance and the least significant difference test in post hoc tests will be used. The Kruskal-Wallis test was use in cases where the variables were skewed. A p-value of <0.05 was considere statistically significant. Multinomial regression logistic model analysis, or multivariate analysis of variance (MANOVA), or analysis of variance (ANOVA), use to determine whether there any statistically significant differences between two or more groups on a set of continuous dependent variables, as appropriate. For quantitative indicators, the distribution pattern (using the Shapiro-Wilk test), mean, standard deviation, median, interquartile range, 95% confidence interval, minimum and maximum values were determined. For categorical and qualitative features, the proportion and absolute number of values determine. Statistical processing performe using the R v4.2 programming language, Python v.3.10 [^R], Statistica 12 program. (StatSoft, Inc. (2014). STATISTICA (data analysis software system), version 12. www.statsoft.com), and IBM SPSS Statistics version 28.0.1.1 (14), 2021, USA. And different models of machine learning model to assess the diagnostic accuracy of the volatile organic compound and the single lead electrocardiography in the diagnosis of ischemic heart disease.
